#### *11.4.3.2 Secondary Efficacy Endpoints*

In line with the secondary endpoints indicated in [Section 7.2](#) (see also [Appendix 5](#)), the secondary efficacy endpoints are:

- Time to response (TTR) defined as the time from start of study treatment to the date of first evidence of response (PR or CR as determined by independent central review per RECIST 1.1);
- Duration of response (DOR) defined as the time from first documented response (PR or CR as determined by independent central review per RECIST 1.1) to either disease progression (as determined by independent central review per RECIST 1.1) or death due to any cause, whichever occurs first. Censoring rules will be similar to those applied for progression-free survival (PFS);
- Disease control rate (DCR), defined as the proportion of subjects who achieved a PR, CR or SD as determined by independent central review per RECIST 1.1;
- PFS defined as the time from start of study treatment to either disease progression (as determined by independent central review per RECIST 1.1) or death due to any cause, whichever occurs first;
- Objective response rate (ORR) in cohort B defined as the proportion of subjects who achieved a partial response (PR) or complete response (CR) at any timepoint as determined by independent central review per RECIST 1.1;
- Overall survival (OS) defined as the time from the start of treatment until death due to any cause;
- ORR, TTR, DOR, DCR and PFS according to local Investigator's review per RECIST 1.1;
- Change in disease-related symptoms as assessed by the Functional Assessment of Cancer Therapy-Kidney Cancer Symptom Index (FKSI-DRS).

All these secondary endpoints will be presented in each cohort separately. In addition, ORR and PFS according to local Investigator's review per RECIST 1.1 as well as OS will be presented in the overall population (cohort A + cohort B).

Below is the definition of the estimand used for the secondary efficacy endpoint of duration of response:

**Treatment:** Cabozantinib

**Population:** Subjects with unresectable, locally, advanced or metastatic RCC with a clear-cell component who progressed after prior CPI therapy with ipilimumab and nivolumab in combination (Cohort A) with a PR or CR at any timepoint during the treatment period.

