#### *11.4.3.4 Secondary Efficacy Endpoint Analyses*

The ORR according to Investigator's assessment (cohort A and cohort B) and by independent central review (cohort B) will be presented with their associated 2-sided 95% CIs using Clopper-Pearson exact method. Discordance in ORR assessed by independent central review and by Investigator will be described.

DCR estimates will be presented in statistical tables with associated 2-sided 95% CIs.

Time-to-event endpoints (TTR, DOR, PFS and OS) will be analysed using the Kaplan-Meier method. The results will be presented for each Cohort A and B both in summary tables and graphically in Kaplan-Meier plots. Kaplan-Meier methodology will be used to characterise the

distribution of endpoints. Median durations and associated 2-sided 95% CIs will be provided. Event rates at timepoints from either first dose of study treatment or first documented response will also be estimated with associated 2-sided 95% CIs.

General censoring rules for the analysis of PFS are described below:

- Subjects who receive non-protocol anti-cancer therapy (NPACT) after start of cabozantinib and before experiencing an event will be right censored at the date of the last tumour assessment prior to the date of initiation of subsequent therapy;
- Subjects who have not experienced an event (and are not otherwise censored) at the time of data cut-off will be right censored on the date of their last tumour assessment;
- Subjects who miss two or more scheduled tumour assessments followed by an event will be right censored on the date of their most-recent tumour assessment prior to the missing assessments.

Additional supportive analyses of PFS will be defined in the SAP using alternative event definitions and censoring schemes to account for partial or completely missing assessments, address bias due to tumour assessment timing, evaluate the impact of potentially informative censoring, and to address potential discrepancies between the documentation of progression per the Investigator and per the independent central review.

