Endpoint : DOR defined as the time from first documented response (PR or CR as determined by independent central review per RECIST 1.1) to either disease progression (as determined by independent central review per RECIST 1.1) or death due to any cause, whichever occurs first.

Intercurrent events :

- Two or more missing scheduled tumour assessment prior to RECIST 1.1 progression (while on treatment strategy)

Subjects will be censored at the date of the last tumour assessment prior to the missing assessment.

- Subjects not treated (while on treatment strategy)

Subjects will not be included in the efficacy analysis.

- Subjects receiving non-protocol anti-cancer treatment prior to RECIST 1.1 progression (while on treatment strategy)

Subjects will be censored at the date of the last tumour assessment prior to the initiation of non-protocol anti-cancer treatment.

SAP Final: Version 6.0: 17 August 2023

- Treatment discontinuation prior to RECIST 1.1 progression (treatment policy strategy)

Subjects will be censored at the date of the last tumour assessment.

- Treatment discontinuation without any post-baseline tumour assessment (treatment policy strategy) after the first response to treatment

Subjects will be censored at the time of first documented response.

Population-level summary : median of DOR 2-sided 95% with CI.

3.1.3 *Safety endpoints*

Safety endpoints are adverse events, clinical laboratory test results, vital signs measurements, ECG and physical examination results, and use of concomitant medication.

Summaries of AEs and SAEs will be tabulated by cohort and overall, according to system organ class (SOC) and preferred term (PT) by overall incidence, worst reported severity, and relationship to study treatment. Selected laboratory test results will be summarised by cohort to evaluate worst post-Baseline Common Terminology Criteria for Adverse Events (CTCAE) grade, as well as shifts or changes from Baseline.

3.1.4 *Multiplicity*

No multiple testing will be performed in this study as no statistical testing will be carried out at the interim analysis for efficacy endpoints.

3.1.5 *Significance testing and estimation*

ORR (primary endpoint) will be tested at the final analysis as described in Section 3.2.1.1 using the one-sided significance level (alpha) of 0.025. No statistical testing will be carried out at the interim analysis for efficacy endpoints.

3.2 *Analysis methods*

3.2.1 *Efficacy*

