In case of response and a partial initial response date, missing day will be imputed by the last day of the month. This will be the most conservative approach considering the latest date for the response. It will be imputed by the first study drug intake in case the first study drug intake is earlier than the imputed date.

In case of censoring and a partial last tumour assessment date, missing day will be imputed by the first day of the month. It will be imputed by the first study drug intake in case the first intake is later than the imputed date. The censoring may occur earlier than the exact date.

(3) Duration of response (DOR)

DOR is defined as the time from first documented response (PR or CR) to either disease progression or death due to any cause, whichever occurs first. DOR will be analysed for responding subjects only. For responding subjects (i.e. subjects with a PR or CR) who are not known to be dead or progressed at the time of data cut-off for DOR analysis, the DOR will be censored at the last tumour assessment and considering the censoring rules defined in the table below.

| Event | Decision | Date of event or censoring |
|---|--------------|---|
| Progressive disease with no more than one missing scheduled tumor assessment before the event and without NPACT before the event. | Not censored | Date of first progressive disease |
| Death with no more than one missing scheduled tumor assessment before the event and without NPACT before the event. | Not censored | Date of death |
| PD or death with two or more missing scheduled tumor assessments before the event | Censored | Date of the last tumor assessment prior to the missing assessment. |
| PD or death with NPACT after the start of cabozantinib and before the event | Censored | Date of the last tumor assessment prior to the date of initiation of NPACT. |
| No event (no PD, no death) with at least one radiological assessment after the first response to treatment. | Censored | Date of last radiological assessment |

SAP Final: Version 6.0: 17 August 2023

| | | |
|---|----------|-------------------------------------|
| No event (no PD, no death) without any radiological assessment after the first response to treatment. | Censored | Date of first response to treatment |
|---|----------|-------------------------------------|

DOT will be calculated as:

DOT(months) = round ((progression date or death date or date of last tumour assessment – date of initial response+1) / (30.4375),0.01)

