In case of non-censoring and a partial progression/death date, missing day will be imputed by the first day of the month. This will be the most conservative approach considering that the earliest date for progression/date. It will be imputed by the date of initial response in case the date of initial response is later than the imputed date.

In case of censoring and a partial last tumour assessment date, missing day will be imputed by the first day of the month. It will be imputed by the date of initial response in case the initial response is later than the imputed date. The censoring may occur earlier than the exact date.

(4) Time-to-Progression for Progression-Free Survival (PFS) analysis

PFS is defined as the time from start of study treatment to either disease progression (as determined by independent central review per RECIST 1.1) or death due to any cause, whichever occurs first. For subjects who are not known to have died or progressed at the time of data cut-off for PFS analysis, the PFS will be censored at the last tumour assessment and considering the censoring rules defined in the table below.

| Event | Decision | Date of event or censoring |
|---|--------------|---|
| Progressive disease with no more than one missing scheduled tumor assessment before the event and without NPACT before the event. | Not censored | Date of first progressive disease |
| Death with no more than one missing scheduled tumor assessment before the event and without NPACT before the event. | Not censored | Date of death |
| PD or death with two or more missing scheduled tumor assessments before the event | Censored | Date of the last tumor assessment prior to the missing assessment. |
| PD or death with NPACT after the start of cabozantinib and before the event | Censored | Date of the last tumor assessment prior to the date of initiation of NPACT. |
| No event (no PD, no death) with at least one radiological | Censored | Date of last radiological assessment |

SAP Final: Version 6.0: 17 August 2023

| | | |
|---|----------|-----------------------------------|
| assessment after the initiation of study treatment. | | |
| No event (no PD, no death) without any radiological assessment after the initiation of study treatment. | Censored | Date of first cabozantinib intake |

PFS will be calculated as:

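### SAP Appendix 1 censors PFS and DOR before new anticancer therapy only when PD or death follows, contrary to the protocol; the curves can only rise or stay the same

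*SAP*

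**What the plan says.** **Protocol, PFS (11.4.3.4).** The NPACT rule opens: "Subjects who receive non-protocol anti-cancer therapy (NPACT) after start of cabozantinib and before experiencing an event will be right censored at the date". Censoring is thus placed at the final scan preceding the new therapy, and no later event is required. The cut-off rule comes second: "Subjects who have not experienced an event (and are not otherwise censored) at the time of data cut-off will be right censored" at the last scan. The words in parentheses give the NPACT rule precedence.

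**Protocol and SAP, DOR.** Protocol 11.4.3.2 ties DOR censoring to the PFS rules. The DOR estimand in Protocol 11.4.3.2 and SAP 3.1.2 has its own entry for NPACT before progression: "Subjects will be censored at the date of the last tumour assessment prior to the initiation of non-protocol anti-cancer treatment". Again no later event is required.

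**SAP, derivation tables (Appendix 1 (3) and (4)).** In each table the only row that censors for NPACT is "PD or death with NPACT after the start of cabozantinib and before the event". The no-event rows carry no NPACT exception. The PFS row begins "No event (no PD, no death) with at least one radiological" and the DOR row reads "No event (no PD, no death) with at least one radiological assessment after the first response to treatment". Both censor at the last radiological assessment.

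SAP 3.2.1.2 refers the reader to Appendix 1 (4) for the PFS censoring rules, and the SAP body does not repeat the protocol's NPACT sentence. SAP Section 5 does not mention the difference.

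**The concern.** Under the SAP tables, how time after the start of NPACT is treated depends on how that time ends. If it ends in PD or death, it is discarded and the subject is censored before NPACT. If it is event-free at cut-off, it is kept up to the last scan. Event-free follow-up under another treatment then counts towards PFS or DOR on cabozantinib, while events under that treatment do not.

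At stake are the main PFS and DOR curves and their landmark rates, and occasionally a median. DOR is the more exposed of the two because it is analysed in responders only, so each subject carries more weight.

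**Working it through.** **Step 1. Compare the rules for a subject who starts NPACT before any event.**

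| Later course | Protocol 11.4.3.4 (PFS); DOR estimand | SAP Appendix 1 (3) and (4) |
|---|---|---|
| PD or death follows | Last scan before NPACT | Last scan before NPACT |
| No PD or death by cut-off | Last scan before NPACT | Last radiological assessment, before or after NPACT |

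Only the second line differs. The row for two or more missed scans also depends on a later event, but the protocol words it the same way, so there is no conflict there.

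**Step 2. Can scans after NPACT exist?** Yes. Protocol 5.2.3 and SAP 1.3.2.1 continue tumour assessment after cabozantinib stops without radiographic progression, until the investigator confirms progression. NPACT is not named as a stopping point.

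**Step 3. Direction.** The Kaplan-Meier estimate is S(t) = product over event times of (1 − d/n), with d events among n at risk. Both rules keep the same events, because events after NPACT are removed under both. The SAP rule only moves some censoring dates later. So d is unchanged and n is equal or larger at every event time, and the SAP curve lies on or above the protocol curve.

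**Step 4. Worked example (hypothetical, 10 subjects).** Five have events at months 3, 3, 6, 6 and 9 without NPACT. Five start NPACT at month 4, with the last prior scan at month 3. Of these, two progress at month 9 (censored at 3 under both rules) and three are event-free at a last scan at month 15 (censored at 3 under the protocol, at 15 under the SAP).

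| Month | Protocol: d/n, S | SAP: d/n, S |
|---|---|---|
| 3 | 2/10, 0.800 | 2/10, 0.800 |
| 6 | 2/3, 0.267 | 2/6, 0.533 |
| 9 | 1/1, 0 | 1/4, 0.400 |

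The median is 6 months under the protocol and 9 under the SAP. The example shows the mechanism, not a likely size.

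**Step 5. Plausible size.** The documents state no figure to reproduce and give no NPACT rate. A simulation used these inputs from the documents:
- 68 evaluable subjects (Protocol synopsis, sample size);
- scans every 12 weeks (SAP 1.3.2.1), or 84/30.4375 = 2.76 months;
- median PFS 7.4 months (METEOR cabozantinib arm, Protocol 1.2.1.1).

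The rest are assumptions: 10 months as a higher median, exponential PFS, follow-up of 12 to 28 months, 5% to 30% starting NPACT before PD, NPACT timing independent of PFS, and scans continuing after NPACT. There were 400 replicates per scenario.

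| True median (months) | NPACT before PD | Mean number with NPACT and no event | PFS at 11.5 months, protocol → SAP | Median PFS, protocol → SAP |
|---|---|---|---|---|
| 7.4 | 5% | 1.1 | 35.9% → 36.4% | 8.28 → 8.28 |
| 7.4 | 10% | 2.1 | 35.8% → 36.8% | 8.28 → 8.28 |
| 7.4 | 20% | 4.2 | 35.2% → 37.6% | 8.28 → 8.28 |
| 7.4 | 30% | 6.3 | 35.6% → 39.8% | 8.28 → 8.28 |
| 10 | 5% | 1.2 | 46.3% → 46.7% | 11.04 → 11.04 |
| 10 | 10% | 2.6 | 46.8% → 47.8% | 11.04 → 11.04 |
| 10 | 20% | 5.1 | 46.3% → 48.4% | 11.04 → 11.04 |
| 10 | 30% | 7.8 | 46.7% → 50.2% | 11.04 → 13.80 |

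The SAP curve never fell below the protocol curve in any replicate. The median moved in one scenario of eight, by one scan interval (13.80 − 11.04 = 2.76 months). For scale, a simple binomial 95% interval at 36% with 68 subjects is ±1.96 × √(0.36 × 0.64/68), about ±11 points.

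**The case against.** **The effect may be small or absent.** It needs NPACT, a later scan, and no PD or death by cut-off, all in the same subject. Off-treatment scanning is required only for subjects who stopped without radiographic progression. A subject who stops for investigator-assessed PD has no required later scan, so the two rules usually give the same date. This stands. A reader might infer that PFS and DOR are materially inflated, but the documents give no count from which to say so.

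**The retained time is not only that of patients who do well on the new therapy.** A reader might infer that it is. Event-free subjects also include those who started NPACT shortly before cut-off, or who were then lost to follow-up. The objection stands.

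**Planned supportive analyses expose part of it.** SAP 3.2.1.2 plans a first supportive PFS analysis that counts events after NPACT, which removes the asymmetry in the other direction. A third adds censoring before treatment discontinuation for subjects who stopped for reasons other than PD or death. Protocol 6.3.2 prohibits other systemic anticancer treatment during cabozantinib, so NPACT normally starts after discontinuation, and the third analysis largely removes the effect in that group. It does not reach subjects who stopped for investigator PD that the IRC did not confirm, where a later scan was taken anyway. The SAP states that these analyses are for PFS only, so DOR has none, and the main tables stay as written.

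**The SAP body already holds the right DOR rule.** True. For DOR the fault is a contradiction between the estimand and the appendix, not a missing rule.

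**The SAP may depart from the protocol.** Protocol Section 11 allows this, and requires an amendment only for major changes to the primary endpoint or its analysis. What is missing is a declaration in SAP Section 5.

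**Conclusion.** The conflict is real on the text: PFS contradicts Protocol 11.4.3.4, DOR contradicts the estimand in both documents, and neither departure is declared. The direction follows from the structure of the estimator: the SAP curves lie at or above those under the protocol rule.

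The size is unknown. Under the assumptions in step 5 it is about 0.5 to 4 points of PFS near 12 months, with the median usually unchanged, and it is zero if no affected subject has a scan after NPACT. No size was computed for DOR.

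A reader might also infer that the trial's main conclusion is at risk. It is not: PFS and DOR are secondary endpoints without a formal test (Protocol 11.3), and the ORR test does not use these tables. The point should be corrected because the fix is cheap and restores the sponsor's own rule.

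**What to change.** In SAP Appendix 1 (3) and (4):

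- Reword the NPACT row to: *NPACT after the start of cabozantinib and before any PD or death, whether or not an event follows: censored at the last tumour assessment prior to initiation of NPACT.*
- Add a fallback for PFS: *if there is no post-baseline assessment before NPACT, censored at the date of first cabozantinib intake.* Without it, such a subject would be censored at the baseline scan, which may be up to 28 days before the first dose, giving zero or negative PFS.
- Add a fallback for DOR: *if there is no assessment after first response and before NPACT, censored at the date of first response.*
- Restrict the no-event rows in both tables to subjects without NPACT.

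The first supportive PFS analysis can stay as the sensitivity analysis that ignores NPACT. If the SAP's present rule was intended, declare and justify it in Section 5 and align the DOR estimand with it.

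The cost is a few table rows and a small change to the derivation program. The downside for the sponsor is PFS and DOR estimates that are slightly less favourable, or unchanged.

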#### 5.2.3.1 *Post-treatment Follow-up Period*

During the Post-treatment Follow-up period, subjects will be contacted every 12 weeks ( $\pm 15$  days), starting after the End of Study Treatment visit, to assess survival status and record the receipt of subsequent anti-cancer therapy. During the follow-up period, any SAEs that occur more than 30 days after the date of the last cabozantinib dose, assessed as related to study treatment or study procedures will also be collected and followed until resolution or stability according to the Investigator. These assessments will be continued until the subject expires or until the end of the study (18 months after the last subject included in the study received the first cabozantinib dose, [Section 5.6](#)), whichever occurs first. Every effort will be made to collect these protocol-specific evaluations unless consent to participate in the study is withdrawn. All AEs will be documented and/or followed as described in [Section 8.1.3](#) and [Section 8.1.4](#).

At each contact, the Investigator (or designee) will determine if the subject has died, and if so, record the date and cause of death as best as can be determined. All efforts must be undertaken by the investigational sites to determine the date of death (or the date the subject was last known to be alive at the time of a data cut-off). This may include, but not necessarily be limited to, telephone calls, registered letters, and reviews of local obituaries and government death records. If a subject is lost to follow-up, multiple attempts to contact study subject or designee must be documented in the subject records.

Every effort will be made to perform protocol-specific evaluations unless consent to participate in the study is withdrawn and the subject no longer allows data collection.

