For TTR, DOR, PFS and OS, the imputation rules in case of partial dates are defined in Appendix 1 (2), (3), (4) and (5), respectively.

The most conservative approach will be systematically considered (i.e. if the onset date of an AE/concomitant medication is missing / incomplete, it is assumed to have occurred during the study treatment phase [i.e. a TEAE for AEs] except if the partial onset date or other data [stop date, ...] indicates differently).

A missing/incomplete date of medical history or disease diagnosis will be assumed to have occurred before any study treatment.

If a partial date and the associated information do not allow to state about the assignation to a group / category, all the possible groups / categories will be considered (i.e.: an AE could be assigned to several possible doses at event onset according to its partial onset date and stop date. Particularly an AE with missing start date will be assigned to each dose received before its end date. Similarly, a medication with partial start and stop dates could be considered as prior and concomitant treatment).

Where this is possible, the derivations based on a partial date will be presented as superior inequalities (i.e.: for an AE started in APR2004 after the administration performed on 31MAR2004, the days since last dose will be “ ≥ 2 ”, similarly the duration of ongoing AEs or medication will be “ $\geq xx$ ” according to the start and last visit dates.).

For TEAE flag, the algorithm is defined in Appendix 1 (10) in case of partial start or stop dates. For time from first dose for adverse events, the imputation rules in case of partial dates are defined in Appendix 1 (11).

For prior/concomitant medication flag, the algorithm is defined in Appendix 1 (16) in case of partial start or stop dates.

For time from diagnosis to screening, the imputation rules in case of partial dates are defined in Appendix 1 (17).

For treatment duration on 1st anti-cancer therapy for subgroup analysis (see Section 3.2.16), the imputation rules in case of partial dates are defined in Appendix 1 (18). In case, the duration treatment cannot be derived as <6 months, or ≥ 6 months based on the available data, the subgroup ≥ 6 months will be considered by default.

3.2.4 *Subject disposition*

Listings of treatment batch number and of enrolment scheme and codes will be presented by subject for each cohort (Listings 16.1.6 and 16.1.7).

SAP Final: Version 6.0: 17 August 2023

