$$\text{PFS (months)} = \text{round} ((\text{date of progression or date of death or date of last tumour assessment} - \text{date of first study drug intake} + 1) / (30.4375), .01)$$

In case of incomplete date of first study drug intake, no imputation will be used.

In case of non-censoring and a partial progression/death date, missing day will be imputed by the first day of the month. This will be the most conservative approach considering that the earliest date for progression/death. It will be imputed by the first study drug intake in case the first study drug intake is later than the imputed date.

In case of censoring and a partial last tumour assessment date, missing day will be imputed by the first day of the month. It will be imputed by the first study drug intake in case the first intake is later than the imputed date. The censoring may occur earlier than the exact date.

(5) Time-to-death for Overall Survival (OS) analysis

OS is defined as the time from the start of treatment until death due to any cause. For subjects who are not known to be dead at the time of data cut-off for OS analysis, the OS will be censored at the time they were last known to be alive. OS will be calculated as:

$$\text{OS (months)} = \text{round} ((\text{date of last known alive or death date} - \text{date of first study drug intake} + 1) / (30.4375), .01)$$

| Event | Decision | Date of event or censoring |
|---------------------|--------------|----------------------------|
| Death | Not censored | Death date |
| No event (no death) | Censored | Date of last known alive |

In case of incomplete date of first study drug intake, no imputation will be used.

In case of non-censoring and a partial death date, missing day will be imputed by the first day of the month. This will be the most conservative approach considering the earliest date for the death. It will be imputed by the first study drug intake in case the first study drug intake is later than the imputed date.

In case of censoring and a partial last known alive date, missing day will be imputed by the first day of the month. It will be imputed by the first study drug intake in case the first intake is later than the imputed date. The censoring may occur earlier than the exact date.

SAP Final: Version 6.0: 17 August 2023

(6) Fksi-DRS Total Score

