|---|--|----------------|--|
| | | Character date | Imputed AE start date |
| Day is missing | | | |
| YYYY-MM < YYYY-MM of first dose of study drug | YYYY-MM-01 | 2002-07-XX | 2002-07-01 |
| YYYY-MM = YYYY-MM of first dose of study drug | Min (first dose of study drug, AE end date) or first dose of study drug in case AE end date is missing | 2002-08-XX | Min (2002-08-11, AE end date) or 2022-08-11 in case AE end date is missing |
| YYYY-MM > YYYY-MM of first dose of study drug | YYYY-MM-01 | 2002-09-XX | 2002-09-01 |
| Day and month are missing | | | |
| YYYY < YYYY of first dose of study drug | YYYY-01-01 | 2001-XX-XX | 2001-01-01 |
| YYYY = YYYY of first dose of study drug | Min (first dose of study drug, AE end date) or first dose of study drug in case AE end date is missing | 2002-XX-XX | Min (2002-08-11, AE end date) or 2022-08-11 in case AE end date is missing |
| YYYY > YYYY of first dose of study drug | YYYY-01-01 | 2003-XX-XX | 2003-01-01 |
| Day, month, and year are missing | | | |
| XXXX-XX-XX | Min (first dose of study drug, AE end date) or first dose of study drug in case AE end date is missing | | Min (2002-08-11, AE end date) or 2022-08-11 in case AE end date is missing |

YYYY = non-missing year, MM = non-missing month, DD = non-missing day, XX = missing field.

In case the AE start date is missing, the most conservative approach will be systematically considered and the AE will be considered as a TEAE, except if other data (e.g. end date) indicates differently.

If AE end date is partial, imputation could be done assuming the latest possible date (i.e. last day of month if day unknown, or 31st of December if day and month are unknown).

(11) Time from first study dose for adverse event

If the start date of the adverse event is identical to the date of first administration, then “<1” day will be presented.

The time will be calculated as (AE start date – first administration date)+1 and presented in days.

If the AE start date is partial due to missing day, the time from first dose will be presented as a superior inequality (e.g.: for an AE started in FEB2004 after the first administration performed on 31JAN2004, the time from first dose will be as “≥2” days).

If the first administration date is partial due to missing day, the time from first dose will be presented as a superior inequality (e.g. for an AE started on 01FEB2004 after the first administration performed in JAN2004, the time from first dose will be as “≥2” days).

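### Month-only death dates are set to the 1st of the month without a last-alive bound, so an imputed OS, PFS or DOR event can precede documented survival (minor)

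*SAP*

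**What the plan says.** Three derivations in SAP Appendix 1 share one rule. For OS, item (5) says: "In case of non-censoring and a partial death date, missing day will be imputed by the first day of the month". For DOR and PFS, items (3) and (4) say: "In case of non-censoring and a partial progression/death date, missing day will be imputed by the first day of the month". In all three the SAP describes this as the most conservative approach, on the ground that it takes the earliest date.

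Each derivation has one lower bound. For OS and PFS: "It will be imputed by the first study drug intake in case the first study drug intake is later than the imputed date". For DOR: "It will be imputed by the date of initial response in case the date of initial response is later than the imputed date".

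The body of the SAP adds nothing for these endpoints. Section 3.2.3.2 says only that "the imputation rules in case of partial dates are defined in Appendix 1 (2), (3), (4) and (5), respectively".

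The last-alive date is already collected and used. Protocol section 5.2.3.1 asks sites to establish the date of death or "the date the subject was last known to be alive at the time of a data cut-off". For patients not known to have died, Appendix 1 (5) says "the OS will be censored at the time they were last known to be alive".

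**The concern.** None of the three derivations compares the imputed date with the last-alive date, the last visit or the last progression-free scan. A patient seen alive on 20 March whose death is recorded only as March is given a death on 1 March. A survivor last seen on 20 March is credited with follow-up to 20 March; the patient who died later that month loses 19 days of observed survival.

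The rule also misses its own rationale. The earliest date compatible with the data is 20 March, not 1 March. Elsewhere the SAP does let other records override a default date: for adverse events, Appendix 1 (10) applies its default "except if other data (e.g. end date) indicates differently".

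In PFS and DOR, event status can change as well. Both tables censor a death that follows non-protocol anti-cancer therapy (NPACT). If NPACT starts on 10 March and death is recorded as March, a death imputed to 1 March precedes the therapy. Read on the imputed date, the table then gives an event where it should censor.

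**Working it through.** The plan gives no figure to reproduce. The check applies the SAP formula and then sizes the conflict.

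**1. Worked examples (dates are assumptions).** Months = (event date − start date + 1) / 30.4375, as in Appendix 1.

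| Endpoint | Start | Last documented alive or progression-free | SAP date | SAP result | Bounded at last documented date |
|---|---|---|---|---|---|
| OS | first dose 10 Jan 2022 | alive 20 Mar 2023 | 1 Mar 2023 | 416/30.4375 = 13.67 | 435/30.4375 = 14.29 |
| PFS | first dose 5 Oct 2022 | Week 24 scan 22 Mar 2023 | 1 Mar 2023 | 148/30.4375 = 4.86 | 169/30.4375 = 5.55 |
| DOR | response 28 Dec 2022 | Week 24 scan 22 Mar 2023 | 1 Mar 2023 | 64/30.4375 = 2.10 | 85/30.4375 = 2.79 |

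The imputed death precedes the alive contact by 19 days, and the progression-free scan by 21 days. The largest possible conflict is 30 days (contact on the 31st), or 30/30.4375 = 0.99 month.

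**2. How often, per month-only death.** Contact intervals come from SAP section 1.3.2.1 and Table 2: visits every 4 weeks on treatment, survival contact every 12 weeks afterwards. Assume day of death D is uniform on 1 to 30, and days since last contact are uniform on 0 to 27 or 0 to 83. A conflict needs the last contact on day 2 or later of the month of death.

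- 12-weekly: the sum of (D − 1) over 30 days is 435 conflict pairs; 435 / (30 × 84) = 0.173.
- 4-weekly: one pair drops out because the interval is only 28 days; 434 / (30 × 28) = 0.517.

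**3. How far.** Summing (contact day − 1) over the conflict pairs gives 4495 and 4494. The means are 4495/435 = 10.3 and 4494/434 = 10.4 days.

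**4. Sensitivity.** A simulation with real calendar months and last contact 1 to 28 or 1 to 84 days before death gave 16.4% and 49.2%, with a mean of 10.2 days.

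**5. Separating two effects.** Setting the day to the 1st moves a death by 14.5 days on average, the mean of (D − 1). The missing bound accounts for only part of this: 4495/2520 = 1.8 days with 12-weekly contact and 4494/840 = 5.35 days with 4-weekly visits. The rest belongs to the disclosed first-of-month choice, which the fix keeps.

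**The case against.** The strongest reply is that this is a small detail in a rule that is deliberately unfavourable to the drug. Protocol section 5.2.3.1 requires every effort to establish the date of death, including obituaries and government death records. Section 4.3.1.2 adds public records after loss to follow-up, and section 15.2 provides for queries on missing or inconsistent data. Month-only deaths may therefore be few. OS, PFS and DOR are secondary Kaplan-Meier estimates, and the ORR test does not use these dates. The SAP also openly accepts that censoring on a partial date may come too early.

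All of that stands, and it limits the severity. It does not remove the defect: the SAP expects partial dates, since it writes rules for them, and the written rule can contradict the trial's own records.

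Two limits on reach also stand. The 52% describes conflicts with an on-treatment visit, not with a scan. Scans are 12-weekly, so about 17% is the nearer guide there, and only for deaths without earlier documented progression. Month-only dates also seem more likely in telephone follow-up than on treatment, where fatal adverse events are reported within 24 hours, although deaths from disease progression are exempt from that reporting. The documents do not give the split.

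**Conclusion.** The point holds as a minor one. As written, Appendix 1 (3) to (5) can date a death before documented survival or before a progression-free scan, and can turn an NPACT-censored PFS or DOR record into an event. Per month-only death, about 17% (12-weekly contact) or 52% (4-weekly visits) would be dated before a contact, by about 10 days on average and at most 30. These shares rest on the uniform-date assumption. The documents do not say how many dates are partial, so no effect on a median or event rate can be given.

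A reader might infer three stronger things that the documents do not support:

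- That the defect shortens survival by 14.5 days per affected patient. Most of that comes from the stated first-of-month choice.
- That about half of imputed PFS and DOR deaths would precede a clean scan. The 12-weekly scan schedule rules that figure out.
- That the efficacy claim is inflated. The error shortens times or adds events, so it runs against the drug, and the ORR test is unaffected.

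**What to change.** In SAP Appendix 1 (3) to (5), for a death date with a missing day:

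- Set the imputed date to the latest of the first day of the recorded month, the last documented alive date and the existing floor (first intake or initial response). For PFS and DOR it must also not precede the last progression-free scan.
- Cap it at the last day of the recorded month. Use the last-alive date itself, not the day after: the day after a contact on 31 March would move a March death into April, and would postdate a death on the day of contact. If the last-alive date falls after the recorded month, query the record.
- For a partial progression date apply only the scan bound, because a patient can be alive after progressing.
- Assess the NPACT censoring rule on the bounded date. The therapy start is itself evidence that the patient was alive, so state that a tie counts as therapy before the event.
- Floor partial last-alive and last-scan dates, which are also set to the 1st, at the latest earlier complete date.

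The cost is one sentence per derivation and a small program change. No new data are needed.
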